At the time of this publication the study protocol was approved by all corresponding regulatory authorities and the local ethic committees in Switzerland (BASEC-ID: 2021-00453), Austria (EK Nr: 2136/2021), France (N° de dossier: 21.04056.000061–22014), Germany (Aktenzeichen:

PASTA (Pediatric Arteriopathy Steroid Aspirin) trial

pediatric stroke

Study Protocol

2022-066-f-A) as well as UK (IRAS ID: 305395) and Australia (RCH HREC Reference Number: 78937). The study is registered at ClinicalTrials.gov (NCT04873583).

Patient population

All patients older than 6 months and younger than 18 years with unilateral FCA-i will be screened on admission. The complete eligibility criteria are provided in table 1.

Inclusion criteria	Exclusion criteria
1. Written informed consent (legal representative)	1. Previous stroke
2. Age 6 months to under 18 years	2. Genetic vasculopathies include ACTA2, neurofibromatosis type 1, trisomy 21
3. Randomization possible within 48 hours of diagnosis and maximum 96 hours after symptom onset	3. Moyamoya or sickle cell disease
4. Symptomatic unilateral cerebral arteriopathy (newly acquired neurological deficits of proven ischemia and unilateral stenosis/vessel irregularity on neuroimaging)	4. Craniocervical arterial dissection
5. Female participants age \geq 13: Negative pregnancy test	5. Primary (small vessel) and secondary angiitis of the CNS
	6. Bilateral arteriopathy
	7. Underlying systemic disorders e.g., rheumatological
	8. On steroid treatment at disease onset
	9. Contraindication to corticosteroid treatment
	10. Inability to follow study-procedures
	11. Participation in another interventional study

Table 1: Eligibility criteria

PASTA (Pediatric Arteriopathy Steroid Aspirin) trial

pediatric stroke

Study Protocol

The diagnosis of unilateral cerebral arteriopathy (inclusion criterion 4) will be made on site by the respective study team. If the diagnosis is not clear, the sponsor will be contacted to review the MRI images together with the neuroradiologists at the sponsor's site. Subsequently, the sponsor and study site will seek a joint agreement as to whether or not the patient fulfills the eligibility criteria.

Randomization and blinding

Allocation will be done in a 1:1 ratio of standard care alone (including aspirin) or standard care plus corticosteroids (See Fig. 3) using web-based randomization with secuTrial.

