Probabilistic minimization will be used, accounting for the following stratification factors: age (6 months through 5 years, 6 years through 11 years, 12 years to under 18 years) and pediatric National Institute of Health Stroke Scale (Ped-NIHSS; < 7, 7 to 12, >12).

Trial participants and local data collectors will not be blinded, as steroid treatment causes obvious clinical signs and symptoms. Imaging outcomes will be centrally assessed by blinded neuroradiologists.

The telephone-interview-based assessments of RRQ (Recurrence and Recovery Questionnaire), mRS (modified Rankin Scale) and VABS (Vineland Adaptive Behavior Scales) will be performed

PASTA (Pediatric Arteriopathy Steroid Aspirin) trial

pediatric stroke

Study Protocol

blinded centrally for all study participants.

Intervention

Participants in both study arms will be treated based on standard care, including antithrombotic treatment with daily oral aspirin (3-5mg/kg/day, maximum 150mg/day). The hyperacute treatment (including intravenous thrombolysis and endovascular thrombectomy) may be performed according to local protocol. Start with any type of anticoagulation is possible and should be done as by local protocol. Switch or start of aspirin is mandatory at latest at inclusion. Suggestions (see supplementary) for standard care are given to the sites but noncompliance is not a deviation to the protocol. These suggestions have been discussed and approved by the international steering committee of the PASTA trial (see Appendix 1).

In addition, participants in the treatment arm will receive 3 days of intravenous methylprednisolone 30mg/kg/day (max. 1000mg/dose) in one daily dose. This is followed by therapy with oral prednisolone 1 mg/kg/day (max. 40mg/day) for 2 weeks and 0.5mg/kg/day (max. 20mg/day) for another 2 weeks.

Outcomes

The Primary Outcome is the change in FCASS from baseline examination to 1 month. In

PASTA (Pediatric Arteriopathy Steroid Aspirin) trial

Pediatr Stroke. 2023;6: 21-42

www.pediatricstrokejournal.com

addition, various imaging data, clinical and safety outcomes will be assessed (see table 2).

Primary Outcome

● Change in FCASS from baseline to 1 month
Secondary Outcomes
Imaging

● Change in FCASS from baseline to 6 months● Volume of stroke (in FLAIR and DWI-sequences) at baseline, 1, 3 and 6 months by modified pediatric ASPECTS● Residual arteriopathy at 6 months by FCASS
Clinical

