
● Functional impairment outcome by PSOM at 1, 3, 6 and 12 months● Recovery by RRQ at 1, 3, 6, and 12 months● Degree of disability or dependence by mRS at 1, 3, 6, and 12 months● Adaptive function by VABS at 6 and 12 months● For children aged >2 years, quality of life at 12 months, by PSQLM● Neurocognitive outcome at 12 months
Mixed clinical/imaging

● Stroke recurrence assessed at 1, 6 and 12 months defined as:
- New focal neurological deficit(s) or- Worsening of the neurological deficits by > 4 pedNIHSS points lasting for more than 24 hours with new or increased diffusion restriction in the corresponding vascular territory, or- New areas of clinically silent infarction, remote from the initial infarct
Safety Outcomes

● Late diagnosis of progressive large to medium vessel childhood primary angiitis of the CNS● Adverse events (abnormal blood pressure, abnormal blood glucose, behavioral problems, infections, gastrointestinal irritation, electrolyte abnormalities requiring

PASTA (Pediatric Arteriopathy Steroid Aspirin) trial

intervention or weight gain)

- Infectious episodes requiring hospitalization
- Serious adverse events related to the study intervention requiring medical intervention

Table 2: Outcome Measures. FCASS: Focal cerebral arteriopathy severity score; ASPECTS: Alberta stroke program early CT score, PSOM: Pediatric Stroke Outcome Measure; RRQ: Recurrence and Recovery Questionnaire; mRS: modified Rankin Scale; VABS: Vineland Adaptive Behavior Scale; PSQLM: Pediatric Stroke Quality of Life Measure; ped NIHSS: pediatric National Institute of Health Stroke Scale.

Imaging Outcomes

Magnetic resonance imaging and angiography (MRI/MRA) will be performed at baseline, 1 and 6 months and, if clinically indicated at 3 months. The imaging protocol will comprise at least DWI/ADC, FLAIR, T2-weighted, time of flight (ToF) MR angiography and SWI sequences. At baseline neck vessel and vessel wall imaging should be considered. MRIs should be performed at 3 Tesla and without sedation or anesthesia if possible. All images will be assessed centrally by two independent neuroradiologists.

The degree of arterial stenosis at different time points is measured using FCASS in MRA.

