Central data monitoring and validation will be performed according to a separate monitoring plan continuously for each site. This will include regular verification of the completeness, accuracy, and plausibility of the entered data and to query the site and follow up anything requiring clarification. No interim analyses are planned and no safety stopping points are defined.

Sample size estimates

For 13 patients of a retrospective study the standard deviation of the change in FCASS from baseline to maximum severity of arteriopathy was 2.8.¹⁴ Based on this standard deviation and a two-sample means test, 64 patients (32 in each group) are required to detect a difference of 2.0 with a power of 80% at a two-sided alpha-level of 0.05.

PASTA (Pediatric Arteriopathy Steroid Aspirin) trial

pediatric stroke

Study Protocol

To account for dropouts (8%), we will enlarge the sample size to 70 patients (35 in each group).

Statistical Analyses

The primary analysis will follow the intention-to-treat (ITT) principle. The primary outcome and secondary continuous variable outcomes that are measured multiple times during follow-up will be assessed in a repeated-measure, mixed-effects linear model.

Neurocognitive outcomes measured at 1 year will be analyzed using a mixed-effects linear model, binary outcomes (recovery, residual arteriopathy) will be assessed using generalized linear mixed-effects models, Time-to-event outcomes (stroke recurrence, infection requiring hospitalization, progressive arteriopathy) will be analyzed using Cox-regression, accounting for the stratification factors used at randomization (country and baseline FCASS).

We will perform a subgroup analysis according to baseline FCASS (<8 vs ≥8), accompanied by an appropriate test of interaction. Moreover, we will test whether the baseline FCASS (used continuously) has an influence on the association between steroid treatment and modified ASPECT score, i.e. whether there is effect modification (interaction).

Scores measured repeatedly over time (FCASS, mRS, PSOM, VABS, modified pediatric ASPECT) might be considered as categories. Patients may shift from category to category several times

PASTA (Pediatric Arteriopathy Steroid Aspirin) trial

pediatric stroke

Study Protocol

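### Table 2 lists the baseline scan among the outcome values for stroke volume and names no baseline-adjusted comparison; using baseline ASPECTS as a covariate would gain precision at no cost

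*Protocol*

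**What the plan says.** Table 2 (Secondary Outcomes, Imaging) gives stroke volume as "Volume of stroke (in FLAIR and DWI-sequences) at baseline, 1, 3 and 6 months by modified pediatric ASPECTS". No change from baseline and no comparison between arms is named.

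The neighbouring outcomes are set out differently:

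- The primary outcome is "Change in FCASS from baseline to 1 month", and the first secondary imaging outcome is "Change in FCASS from baseline to 6 months". Baseline is the reference in both.
- "Residual arteriopathy at 6 months by FCASS" is a level, but at a follow-up visit only.
- Repeated clinical outcomes start after baseline, for example "Functional impairment outcome by PSOM at 1, 3, 6 and 12 months".

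Stroke volume is therefore the only outcome in Table 2 with a baseline value among its outcome time points.

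The Statistical Analyses section says that "secondary continuous variable outcomes that are measured multiple times during follow-up will be assessed in a repeated-measure, mixed-effects linear model". It does not say what part a baseline score plays in that model. The only adjustment it names is for stratification factors, and baseline ASPECTS is not one of them. The section also plans to test whether baseline FCASS "has an influence on the association between steroid treatment and modified ASPECT score", and it lists modified ASPECTS among the scores for the ordered logistic shift analysis.

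**The concern.** Entry requires "newly acquired neurological deficits of proven ischemia and unilateral stenosis/vessel irregularity on neuroimaging", so the index infarct is already there when the child is randomized. Modified ASPECTS gives one point to each abnormal area (Imaging Outcomes). A follow-up score therefore carries the index infarct together with any later injury, and only the later part can respond to steroids.

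Two things follow. A pre-treatment value cannot show a treatment effect, so its place among the outcome values needs explaining. And if follow-up levels are compared without regard to the index infarct, differences between children in its size remain as noise. Minimization uses age and Ped-NIHSS, not infarct extent, so with about 32 children per arm some chance imbalance in index infarct is to be expected.

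At stake is the precision of the trial's imaging measure of brain injury, and of the interaction test and shift analysis that use the same score.

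**Working it through.** **The plan's own figure.** The Sample size section uses SD 2.8, difference 2.0, power 80% and two-sided alpha 0.05. The normal formula gives 2 × (1.960 + 0.842)² × (2.8/2.0)² = 30.8, so 31 per arm. The t-test gives 31.76, so 32 per arm and 64 in total. Then 64/0.92 = 69.6, so 70. The stated figures reproduce. They concern FCASS; the protocol gives no figure for stroke volume.

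**Inputs for the check.**

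- 32 per arm (Sample size section), complete data.
- Scheduled scans at baseline, 1 and 6 months (Imaging Outcomes).
- Assumed: equal variance at each visit (set to 1) and one correlation ρ between any two visits. The protocol gives no ρ, so 0.3 to 0.9 is shown.
- Assumed: no effect at baseline and a constant effect afterwards.
- Inferred from the entry criteria: the baseline scan precedes randomization.

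**Formulas.** With m = 2 follow-up scans, the variance per child is:

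- mean follow-up level, unadjusted: (1 + (m − 1)ρ)/m = (1 + ρ)/2
- the same, adjusted for baseline: (1 + ρ)/2 − ρ²
- mean follow-up minus baseline (change score): (1 + ρ)/2 + 1 − 2ρ = 1.5(1 − ρ)

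The standard error of the arm difference is √(2 × variance/32). Example at ρ = 0.7: unadjusted √(2 × 0.85/32) = 0.230; adjusted √(2 × 0.36/32) = 0.150; change √(2 × 0.45/32) = 0.168.

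| ρ | SE, levels unadjusted | SE, adjusted for baseline | Reduction by adjustment | SE, change score |
|---|---|---|---|---|
| 0.3 | 0.202 | 0.187 | 7% | 0.256 |
| 0.5 | 0.217 | 0.177 | 18% | 0.217 |
| 0.7 | 0.230 | 0.150 | 35% | 0.168 |
| 0.8 | 0.237 | 0.127 | 46% | 0.137 |
| 0.9 | 0.244 | 0.094 | 62% | 0.097 |

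A model that keeps baseline in the response vector, with treatment-by-time terms and one common baseline mean, gives the same standard errors as the adjusted column and an undiluted effect.

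The adjusted analysis is better than unadjusted levels at every ρ tried. The change score is worse than levels at 0.3, equal at 0.5 and better above that, and it never beats adjustment.

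**Illustration in power.** For an assumed true effect of 0.4 SD (no source in the protocol), unadjusted levels give 51%, 46%, 41% and 39% at ρ = 0.3, 0.5, 0.7 and 0.8. Adjustment gives 57%, 62%, 76% and 88%.

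**If one treatment effect were pooled over all visits including baseline.** With k visits, one of which carries no effect, the pooled effect is (k − 1)/k of the true one: 2/3 with baseline, 1 and 6 months, and 3/4 if 3 months is added.

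**The case against.** The strongest reply is that the protocol never states a harmful model. Table 2 may simply list when stroke volume is scored, and the Statistical Analyses section names only a model family. Keeping baseline in the response vector of a repeated-measures model is ordinary practice and, with a common baseline mean, among the most efficient choices. Whether baseline is a response, a covariate or a constrained mean is often left to the SAP, which is not at hand.

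Most of this stands. A reader might infer that the plan dilutes the steroid effect. The documents do not support that, because dilution needs a single treatment term pooled over baseline and follow-up, and no such term is written. A reader might also infer that the two sections contradict each other. They do not: the reference to outcomes measured during follow-up is a general sorting phrase, and its sentence also covers the primary outcome, which itself uses the baseline scan. Nor are levels an error. Randomization makes follow-up levels comparable, chance imbalance costs precision without biasing the comparison, and the same table uses FCASS as a level at 6 months. New injury is also captured separately under stroke recurrence.

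What remains is the outcome definition itself. Table 2 is the protocol's own list of outcomes. For this outcome alone it places a pre-treatment value among the outcome values, with no comparison attached.

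**Conclusion.** The point holds as a low-cost improvement to the definition of one secondary outcome. As written, the role of the baseline score is open, and a plain comparison of follow-up levels would be a permissible reading. That reading is unbiased but less precise than it need be: baseline adjustment would cut its standard error by about 7% to 62% for ρ from 0.3 to 0.9.

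The size rests on the assumed ρ, equal correlation between visits, complete data on 32 per arm, and a comparison otherwise unadjusted. If the model already adjusts for baseline FCASS, which the Introduction says correlates with stroke volume, part of the gain may already be secured. The shrinkage to 2/3 or 3/4 is a conditional warning about one possible model, not a description of the plan. The primary analysis and the sample size are unaffected.

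**What to change.** In Table 2, define the outcome as modified pediatric ASPECTS at the scheduled follow-up scans, 1 and 6 months, compared between arms. In Statistical Analyses, state that baseline ASPECTS enters the mixed model as a covariate or through a common baseline mean, and use the same adjusted outcome in the test of interaction with baseline FCASS.

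Do not rely on an unadjusted change score, which is less precise than levels when ρ is below 0.5. Once baseline is a covariate, level and change give the same treatment estimate, so the covariate is the part that matters.

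Table 2 also lists stroke volume at 3 months, whereas Imaging Outcomes has a 3-month scan only where there is a clinical indication. The two places must be reconciled. Basing the comparison on the visits at which every child is due a scan keeps it free of a selected subset.

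The cost is one line in Table 2 and one sentence on the model. Baseline images are already read centrally, so no new data are needed.

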Nevertheless, the study has some limitations. The diagnosis of FCA-i remains challenging in the acute setting for the following reasons: According to the traditional definition, the disease is monophasic - this cannot be detected in the acute situation. Imaging findings often overlap with intracranial dissection, so that differentiation is often difficult. Moyamoya is differentiated from FCA-i by the presence of collateral vessels. However, these may be absent in early stage moyamoya.³¹ Biomarkers such as varicella serology in CSF are only effective in certain cases.³² In recent years, vessel wall imaging has been increasingly used as a diagnostic biomarker.³³ However, vascular wall imaging with contrast enhancement cannot be performed within a study setting for ethical reasons. Overall, the diagnosis is therefore still often based on expert opinion by experienced stroke specialists. Accordingly, the inclusion criteria for this study were defined more broadly - so that the presence of unilateral arteriopathy after exclusion of any differential diagnoses is sufficient. As a support the centers will be guided in diagnosis by the sponsor team and their neuroradiologists experienced in this diagnosis.

As FCA-i is a rare disease, the number of cases in each center included in the study is very low. This means that the experience of the investigators of the individual centers in handling the study will be low and stratification by center is not possible. This and the lack of complete blinding of the investigators increases the risk of observer bias. Since the imaging outcomes and

PASTA (Pediatric Arteriopathy Steroid Aspirin) trial

Pediatr Stroke. 2023;6: 21-42

www.pediatricstrokejournal.com

thus the primary outcome are collected centrally, they are not affected by this risk. To reduce risk in recording clinical outcomes, investigators were provided with videos for learning the ped-NIHSS and PSOM in a standardized manner. In addition, the collection of various clinical outcomes is done centrally via telephone interview by a blinded investigator. As a further limitation, it should be mentioned that a surrogate marker was chosen as the primary outcome here. However, it could be shown that this correlates with the clinical outcome and that this has a high reliability.^{12,14} In addition, to validate the results of the primary outcome, various clinical outcomes will also be assessed in the PASTA study.

Summary and conclusion

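### Stroke volume is listed as a 3-month outcome, but the 3-month MRI is done only if clinically indicated, so a 3-month comparison would rest on a selected subset whose selection can differ by arm

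*Protocol*

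**What the plan says.** Protocol, Table 2 (secondary imaging outcomes): "Volume of stroke (in FLAIR and DWI-sequences) at baseline, 1, 3 and 6 months by modified pediatric ASPECTS".

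Protocol, Imaging Outcomes: "Magnetic resonance imaging and angiography (MRI/MRA) will be performed at baseline, 1 and 6 months and, if clinically indicated at 3 months".

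On blinding, the Randomization and blinding section says "Trial participants and local data collectors will not be blinded, as steroid treatment causes obvious clinical signs and symptoms" and "Imaging outcomes will be centrally assessed by blinded neuroradiologists". The Discussion concedes, partly because centres have few cases: "This and the lack of complete blinding of the investigators increases the risk of observer bias". It then holds that the imaging outcomes escape this risk because they are collected centrally.

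On analysis, the Statistical Analyses section says that "secondary continuous variable outcomes that are measured multiple times during follow-up will be assessed in a repeated-measure, mixed-effects linear model". It adds an ordinal mixed model (shift analysis) for repeatedly measured scores and names FCASS and modified ASPECTS among them. Nothing there separates scheduled scans from clinically indicated ones.

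**The concern.** Stroke volume is scored from FLAIR and DWI images, so a child without a 3-month scan has no 3-month value. The protocol thus names an outcome that its own schedule does not collect from every child. Whether a value exists depends on a clinical judgement about the child's condition.

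That selection can differ between arms in two ways. First, those who judge the need for a scan may know the allocation. Second, even under one impartial rule, an effective treatment would leave fewer treated children meeting the indication. Central blinded reading protects the score given to a scan, not the decision to obtain it.

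At stake is the 3-month time point of one secondary outcome, and any repeated-measures imaging model that takes in indicated scans as ordinary observations.

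**Working it through.** **1. The passages side by side.**

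| Imaging outcome in Table 2 | Times | Scheduled scan for every child? |
|---|---|---|
| Change in FCASS (primary) | baseline, 1 month | yes |
| Change in FCASS | baseline, 6 months | yes |
| Residual arteriopathy | 6 months | yes |
| Stroke volume | baseline, 1, 6 months | yes |
| Stroke volume | 3 months | no, only if clinically indicated |

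One cell is out of line.

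**2. Inputs for an illustration.** The protocol gives no 3-month scan rate, and no standard deviation or expected effect for modified ASPECTS. From Sample size estimates I borrow the FCASS difference of 2.0 and SD of 2.8, as a scale only. These reproduce the protocol's own figure: 2 × (1.96 + 0.842)² × (2.8/2.0)² = 30.8 per arm by the normal formula, and 31.76, so 32, by the t-test. That gives 64 in total; 64/0.92 = 69.6, so 70.

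Assumed: 30% of children scanned overall; correlation r = 0.5 to 0.7 between indication and current severity; correlation 0.6 to 0.9 between visits.

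**3. Effective treatment, one scanning rule in both arms, scanned children only.** Let the indication be U = r × (severity/2.8) + √(1 − r²) × noise, with a scan if U > c. Severity has mean 0 on control and −2.0 on steroid, so U is lower by r × 2.0/2.8 on steroid. The mean severity of scanned children is the arm mean plus r × 2.8 × φ(t)/P(U > c), where φ is the standard normal density and t is c on control and c + r × 2.0/2.8 on steroid. The threshold c is set so that the two scan rates average 30%.

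- r = 0.5: c = 0.354; scan rates 36% control, 24% steroid. Means: 1.4 × 1.036 = 1.45 and −2.0 + 1.4 × 1.299 = −0.18. Difference 1.63, 18% too small.
- r = 0.7: c = 0.291; scan rates 39% and 21%. Means: 1.96 × 0.992 = 1.94 and −2.0 + 1.96 × 1.360 = 0.67. Difference 1.28, 36% too small.

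Here r is a within-arm correlation. With r defined over both arms together, simulation gives about 1.7 to 1.3. The range is therefore about 15-35%.

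**4. The same setting after mixed-model-type adjustment.** As a stand-in for a mixed model with visit-specific effects, the 3-month score is regressed on the baseline, 1- and 6-month scores in scanned children and predicted for all. The simulated 3-month difference is about 1.6 to 2.0 against a true 2.0, about 2-20% too small. With r defined within arm and the regression fitted separately by arm, it is 1.52 to 1.94, or 3-24% too small. The bias is smallest when visits are highly correlated.

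**5. No treatment effect** (simulation, r = 0.5 to 0.8). With 30% scanned in each arm by the same rule, the 3-month mean of scanned children is 0.58 to 0.93 SD too high, but the bias between arms is about 0. If control and steroid scan rates are 30/20%, 40/20% or 50/30%, a false difference of 0.12 to 0.35 SD appears among scanned children, and 0.02 to 0.25 SD remains after adjustment. With fewer scans on steroid it runs against steroid; the reverse imbalance would turn it round.

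**6. Precision.** The detectable difference at 80% power is 2.80 × √(2/k) SD with k scanned children per arm. For k = 32 it is 0.70 SD. If 30% are scanned, k = 9.6 and it is 1.28 SD (normal approximation, optimistic at this size).

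**The case against.** The strongest reply is that the consequence is small and partly unproven. Much of this stands.

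- **Selection by arm.** A reader might infer that the scanned subset does differ by arm. The documents do not say so. They neither define the indication nor name who decides; the sentence on blinding concerns participants and local data collectors. That unblinded site staff decide is a sound inference, not a statement. With no treatment effect and one rule, the between-arm bias is about nil. The supported wording is that selection can differ.
- **The mixed model.** A reader might infer that it offers no protection. That is too strong. If scanning depends only on arm and scores already in the model, the data are missing at random and a correctly specified likelihood analysis is valid. Bias remains only so far as the decision depends on the unobserved 3-month state. That is plausible for a scan prompted by how the child is now, but not established.
- **The figures.** They are borrowed from FCASS, and the FCASS standard deviation is itself for change to maximum severity. They are not estimates for modified ASPECTS, a score from 0 to 30.
- **FCASS and the primary outcome.** A reader might extend the point to these. Every FCASS outcome in Table 2 falls on a scheduled scan. Which visits enter each model is commonly left to the SAP, which is not shown.

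What the reply does not remove is the mismatch itself. No analysis plan can supply scans that were never scheduled.

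**Conclusion.** The concern holds as an inconsistency between Table 2 and the imaging schedule, confined to the 3-month time point of one secondary outcome. A comparison of the arms there would rest on a clinically selected subset, with selection that can differ by arm, and neither blinded reading nor the mixed model fully cures this.

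The sizes in the working are conditional on an effective treatment, 30% scanned and the assumed correlations; they show an order of magnitude, not a forecast. In that setting the error shrinks a real effect. A spurious difference needs scan rates or rules that differ by arm.

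The primary analysis at 1 month has a scheduled scan for every child and is not affected in itself. The point should be corrected, but it does not threaten the trial's main conclusion.

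**What to change.** Reconcile Table 2 with the Imaging Outcomes section:

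- Remove 3 months from stroke volume as a between-arm outcome.
- State that the between-arm analyses of modified ASPECTS, linear and ordinal, and any repeated-measures FCASS model use the scheduled baseline, 1- and 6-month MRIs.
- Report clinically indicated 3-month scans descriptively: number by arm, reason for the scan, and scores.

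This changes wording only and leaves when children are scanned as it is. Making the 3-month MRI routine would also remove the mismatch, but that is a clinical decision outside this point. The cost is a 3-month imaging comparison that the schedule cannot support. The protocol paper reports 7 participants randomized, so the change could be made well before analysis.

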a significantly better neurologic outcome¹ and an uncontrolled case series, showed that steroid treatment reduced vessel wall enhancement.¹⁰ In contrast, it has also been postulated that infectious mechanisms may play a role in the pathophysiology of FCA-i, and concerns have been raised about possible adverse effects of steroid treatment on these mechanisms.^{11,12} The mechanism has best been studied for varicella related FCA-i: After systematic infection varicella virus remains in ganglions (“sleeping”). By reactivation there is a neuronal transport of the virus, followed by inflammatory process in the vessel wall.¹³ For other disease-causing microorganisms, the pathophysiology is less clear, but likely similar. Reflective of the resulting uncertainty and equipoise, a Delphi survey of pediatric stroke specialists identified a steroid trial in children with FCA-i as the most important and feasible trial in this research field.⁴

To assess the severity of stenosis and the course of FCA-i in a standardized manner, the Focal Cerebral Arteriopathy Severity Score (FCASS) was developed in 2018. It is calculated based on the degree of arterial stenosis in MR, CT or conventional angiography in five cerebral arterial segments. Consistent with the natural history of FCA-i, FCASS increases in the first months of the disease and then decreases thereafter. The score was shown to be reliable and to correlate with long-term outcome as well as stroke volume.^{12,14}

The objectives of this study are to evaluate if early anti-inflammatory treatment may influence

PASTA (Pediatric Arteriopathy Steroid Aspirin) trial

pediatric stroke

Study Protocol

the course of arteriopathy, improve clinical outcomes, and prevent stroke recurrence in children with FCA-i.

The primary hypothesis is, that children with FCA-i treated with a course of high dose methylprednisolone/prednisolone will show greater improvement of focal stenosis and arteriopathy as measured by FCASS.

Methods

Design

This is a PROBE-study, comparing a high-dose course of intravenous methylprednisolone/oral prednisolone plus standard care versus standard care alone in children with FCA-i. The study will be conducted in 27 centers in Australia, Austria, France, Germany, Switzerland, and the United Kingdom.

Recruitment of participants is planned to occur over a period of 36 months. The data collection is shown in Fig. 2.

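### Read literally, the recurrence definition misses a new remote infarct whose only effect is a 1 to 4 point worsening of an existing deficit, although the same infarct counts if it is silent

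*Protocol*

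**What the plan says.** Protocol, Outcomes, Table 2 (mixed clinical/imaging) introduces the outcome with "Stroke recurrence assessed at 1, 6 and 12 months defined as" and lists three alternatives joined by *or*:

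1. "New focal neurological deficit(s) or"
2. "Worsening of the neurological deficits by > 4 pedNIHSS points lasting for more than 24 hours with new or increased diffusion restriction", in the vascular territory that corresponds
3. "New areas of clinically silent infarction, remote from the initial infarct"

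The Introduction names recurrence among the objectives: early treatment is to be evaluated for whether it may influence "the course of arteriopathy, improve clinical outcomes, and prevent stroke recurrence in children with FCA-i". Under Statistical Analyses, "Time-to-event outcomes (stroke recurrence, infection requiring hospitalization, progressive arteriopathy) will be analyzed using Cox-regression".

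Two other sections matter here. Under Imaging Outcomes, MRI/MRA "will be performed at baseline, 1 and 6 months and, if clinically indicated at 3 months", and all images are read centrally by two independent neuroradiologists. Under Randomization and blinding, imaging assessment is blinded, local data collectors are not, and the assessments listed as blinded and central are RRQ, mRS and VABS. The pedNIHSS is not on that list.

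**The concern.** Criterion 3 admits a new remote infarct only when it is silent. Criterion 2 admits worsening only above 4 points. Between them lies a remote infarct that is neither silent nor severe and that shows only as a mild worsening of a deficit already present. The same lesion without any symptoms would be recorded as a recurrence. It is hard to believe that the authors meant a symptomatic infarct to rank below a silent one.

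Two things are at stake. Events that MRI has established can drop out of a secondary outcome tied to a stated objective. In addition, the lesion is read blind, but whether it counts can turn on a local, unblinded call between no change and slightly worse. That is avoidable in an open-label trial that relies on central reading to limit observer bias.

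**Working it through.** The protocol states no event count, recurrence rate or power for this outcome, so there is no figure to reproduce. The check is one of logic.

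**Inputs.** The three criteria of Table 2, combined by *or*. The case examined is a new infarct remote from the initial one, with diffusion restriction present in the corresponding territory and any worsening lasting more than 24 hours, so that only clinical severity varies. The protocol does not define silent; it is taken here as no new deficit and no rise in pedNIHSS.

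| pedNIHSS rise | New focal deficit? | Criterion 1 | Criterion 2 | Criterion 3 | Counted? |
|---|---|---|---|---|---|
| 0 | no | no | no | yes | **yes** |
| 1, 2, 3 or 4 | no | no | no | no | **no** |
| 5 or 6 | no | no | yes | no | **yes** |
| 1 to 4 | yes | yes | no | no | **yes** |
| 5 or 6 | yes | yes | yes | no | **yes** |

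Without a new focal deficit, the answer runs yes, no, yes as severity rises. The result is the same whether criterion 1 stands alone or is taken to share the 24-hour and diffusion conditions of criterion 2.

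**For comparison, a lesion that is not remote.** With no new deficit, it is uncounted at 0 to 4 points and counted from 5. That is monotone: it is the threshold of criterion 2 doing its job, and it is not part of the gap.

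**Size.** Two of the inputs below are assumptions, because the protocol gives neither.

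- Children per arm: 35 (Sample size estimates).
- Assumed recurrence risk: 20%, range 10 to 30%.
- Assumed share of recurrences that are a 1 to 4 point worsening of an existing deficit: 25%, range 10 to 40%.

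Uncounted events per arm = 35 × risk × share.

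- Central: 35 × 0.20 = 7 events, of which 7 × 0.25 = 1.75 are uncounted.
- Low: 35 × 0.10 = 3.5 events, of which 3.5 × 0.10 = 0.35.
- High: 35 × 0.30 = 10.5 events, of which 10.5 × 0.40 = 4.2.

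The assumed share covers all mild worsening, including growth of the index lesion. Only the remote part belongs to the gap, so for any given pair of assumptions the result is an upper bound. The documents give nothing from which to estimate the remote fraction.

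**The case against.** The strongest reply is that the cell is small. The infarct must be remote, there must be no new focal deficit, an existing deficit must worsen, and the worsening must be 1 to 4 points. Criterion 1 has no points threshold, so any remote infarct that adds a new sign still counts. This stands. A reader might infer that mild symptomatic recurrences in general are lost; the text does not support that.

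A second reply is that criterion 3 is plainly meant as a residual category for new remote infarcts not already caught clinically, and that operational detail can sit in a statistical analysis plan. The intention is plausible, but the wording says otherwise. The protocol itself fixes the definition, and no other section fills the gap. Leaving assessors in 27 centers to read past the word silent, or to relabel mild worsening as a new deficit, invites inconsistency.

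Third, modified pediatric ASPECTS scores abnormal areas whatever the symptoms, and the RRQ asks about recurrence by blinded interview. So the information is partly captured, but neither is named as a route into the recurrence definition.

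Two further inferences are tempting and should be resisted:

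- **That the gap must be common because the disease is unilateral.** Same side does not mean remote, a term the protocol leaves undefined. Extension in the index territory falls under criterion 2.
- **That steroids would falsely appear to prevent recurrence by making events milder.** This needs a different uncounted share in each arm, and nothing in the document supplies or suggests one.

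**Conclusion.** The gap is real on the literal wording and narrow in extent. A new remote infarct counts at 0 points and from 5 points, but not when its sole effect is a 1 to 4 point worsening of an existing deficit. Whether such an infarct counts can rest on an unblinded local judgement, even though the image is read blind.

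The number of affected events cannot be derived from the protocol. The 1.75 of 7 per arm (range 0.35 of 3.5 to 4.2 of 10.5) rests wholly on assumed rates and bounds the gap from above under those assumptions. No bias in the treatment comparison can be quantified or given a direction. The outcome is secondary and the primary analysis is untouched. This is a low-priority correction, worth making because it costs so little.

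**What to change.** In Table 2, remove the silent condition from criterion 3, for example: *New areas of infarction on MRI, remote from the initial infarct, with or without clinical symptoms*. Report silent and symptomatic recurrences separately, so that the clinical content of the outcome stays visible. Leave criterion 2 as it is for the index territory. Overlap between the criteria does no harm, since they are alternatives and an event that meets more than one is still one event.

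The cost is one wording change and the matching derivation. No scans or readings are added, as the existing images are already read centrally and blind. Any recurrence already assessed would need to be re-derived; Trial status reports 7 participants randomized at this version.

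The limit is that the change works only where an MRI exists. Scans are scheduled at 1 and 6 months, and at 3 months if clinically indicated. None is listed at 12 months, although recurrence is assessed then, so the gain after month 6 depends on imaging the protocol does not schedule.
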